# 5.1.2.4 Distant Metastasis-Free Survival (DMFS)

Distant metastasis free survival (DMFS) in months is calculated as (first metastasis new lesion scan date or death date within 2 missed scheduled tumor assessment – date of randomization + 1)/30.4375. Patients without metastasis and death are censored at the date of the last disease assessment. Patients without post-baseline disease assessment are censored at randomization date.

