- b. Patients will be followed with visits every 3 weeks (± 4 days) for 2 years (from Day 0) for until progression. Tumor size will be assessed every 6 weeks for the first year, then every 12 weeks until progression. Patients will then have no further staging procedures. Tumor biopsies will be obtained at 6 months or longer for patients with treatment response. Tumor biopsies will also be obtained at time of progression.
- c. Informed consent and HIPAA authorization must be signed before any screening study-related procedures are initiated. Three informed consents will be used: one to screen tumor sample for NY-ESO-1, one to engage in the study protocol, and an agreement to continue in the study and obtain peripheral blood samples and biopsies if the patient meets the criteria for progressive disease but wishes to remain on study.
- d. Documentation of NY-ESO-1 expression in prior tumor samples may have been collected from any procedure performed before baseline activities. There is no time limit for use of the results from the IMDZ-approved central lab.
- e. Vital sign measurements include temperature, pulse, respiratory rate, and resting systolic and diastolic blood pressure. On the day of each dosing, vital signs will be obtained pre-dosing and 30 minutes after dosing. For the first atezolizumab infusion, the patient's vital signs (HR, respiratory rate, BP, and temperature) should be measured within 15 minutes of the infusion, during the 60-minute infusion (every 15 \pm 5 minutes), and 30 minutes after the infusion. For subsequent infusions, vital signs do not need to be obtained during the infusion if the prior infusion was tolerated without symptoms.
- f. Once the baseline physical exam has been conducted, a simple symptom-directed physical exam should be performed for all subsequent visits. Height and weight will be collected at Day 0 only.
- g. Imaging will be performed by CT scan as defined by RECIST/irRC at screening and every 6 weeks after first study injection for the first year, then every 12 weeks for tumor staging until disease progression and includes a confirmatory scan performed at least 4 weeks later. Magnetic Resonance Imaging (MRI), bone scans, or PET/CT at baseline or subsequent visits will be performed only if clinically indicated.

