6.1 Inclusion Criteria

Patients must meet ALL of the following criteria to be enrolled in the study:

1. Locally advanced, relapsed, or metastatic sarcoma with measurable tumor burden following therapy, as defined by RECIST v1.1; the total of all lesions must be ≤ 12 cm (for synovial sarcoma) or ≤ 15 cm (for myxoid/round cell liposarcoma [MRCL])
2. Tumor histology consistent with synovial sarcoma or MRCL
3. Tumor specimen positive for NY-ESO-1 expression by IHC
4. Inadequate response, relapse, and/or unacceptable toxicity with one or more prior systemic, surgical, or radiation cancer therapies
5. Have resolution of toxic effect(s) of the most recent prior therapy to Grade 1 or less (except Grade 2 or less neuropathy or alopecia). If subject received major surgery or radiation therapy, they must have recovered from the toxicity and/or complications from the intervention.
6. ≥ 18 years of age before the first scheduled dose
7. Eastern Cooperative Oncology Group (ECOG) performance status of 0 or 1
8. Electrocardiogram (ECG) without evidence of clinically significant abnormality
9. If female of childbearing potential (FCBP), willing to undergo pregnancy testing and agrees to use at least 2 adequate barrier contraceptive methods during the dosing period and for 90 days after the last injection of CMB305 or atezolizumab
10. If male and sexually active with a FCBP, must agree to use highly effective contraception such as latex condom during the dosing period and for three months after last CMB305 injection
Note: Abstinence is acceptable for either gender if this is the established and preferred contraception for the subject.

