10.2.2.4.2 Secondary Efficacy Analysis

A secondary efficacy analysis will be based on the proportion of patients that are progression-free at 6 months after start of study drug treatment (Day 0). Each treatment group will be evaluated with a Simon 2-stage design (Section 10.3.1). Time-to-next-treatment and DMFS will be compared between treatment arms based on a stratified log-rank test. The Kaplan-Meier curve will summarize TTNT graphically by treatment arm. Tabular summaries of the Kaplan-Meier curves will be provided by treatment arm.

Immune response and histologic and molecular tissue changes in tumor tissue or peripheral blood will be summarized by treatment arm.

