#### 2.2 Secondary Objective

The secondary objectives are:

- To evaluate the safety of CMB305 in combination with atezolizumab and atezolizumab alone in patients with locally advanced, relapsed, or metastatic sarcoma expressing NY-ESO-1
- To evaluate progression-free survival rates (PFR) at 6 months after start of study treatment
- To evaluate the immune response and histologic and molecular tissue changes in tumor tissue and peripheral blood
- To evaluate the time to next treatment (TTNT)
- To evaluate the distant metastasis free survival (DMFS)

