# 7.6.2.4 Distant Metastasis-Free Survival (DMFS)

DMFS will be analyzed using the same methods described for OS/PFS.

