# 7.7 Subgroup Analysis

The following subgroups will be used for primary PFS and OS analysis in ITT and Efficacy set.

- Excluding safety run-in patients
- Patients with confirmed CR/PR/SD on study
- Patients with unconfirmed CR/PR/SD on study
- Patients with confirmed PD on study
- Type of Sarcoma (Myxoid/Round Cell Liposarcoma and Synovial Sarcoma)
- NY-ESO-1 (%) categories (1-<100, 100)
- NY-ESO-1 (%) categories (1-75, >75-99)
- Age (<48 Years, >=48 Years)
- Sex (Female, Male)
- Baseline ECOG (0, 1)
- Time from Diagnosis (<30.3 months, >= 30.3 months)
- Time from Diagnosis (<18.4 months, 18.4 <46.8 months, >= 46.8 months)
- Disease Status at Study Start (Locally Advanced, Metastatic)
- Metastatic Status (Relapsed/Recurrence of prior metastatic, Relapsed/Recurrence of prior locally advanced)
- Stage at Diagnosis (I/II/III, IV)
- Race (White, Other)
- Progression Status at Screening (SD, PD)
- Number of lines of prior chemotherapy (1, 2, >=3)
- Number of Target/Non-Target Lesions (<=3, >=4)
- Number of Target lesions (<=2, >=3)
- Patient with 1 prior line of chemotherapy and with response SD or better in prior therapy
- Synovial Sarcoma patient with 1 line of chemotherapy and with response SD or better in prior therapy

The below subgroups are defined for PFS analysis only.

- New target lesion on study (Yes, No)
- Total size of target lesion at baseline (0-15 mm, 16-50 mm, > 50 mm)
- Number of organs with target/non-target lesions at baseline (1, 2, >=3)
- Prior Anthracyclines Use (Yes, No)

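### Distant metastasis-free survival is analysed in all randomized patients, including those already metastatic at entry, so the ITT result does not measure what its name says

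*SAP*

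**What the plan says.** DMFS is a secondary objective and endpoint (Protocol 4.1.2 and 4.2.2; SAP 2.2). The Protocol does not define it. Protocol 10.2.2.4.2 says only how it will be compared: "Time-to-next-treatment and DMFS will be compared between treatment arms based on a stratified log-rank test".

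The definition is in SAP 5.1.2.4. The clock starts at randomization and the event is "first metastasis new lesion scan date or death date within 2 missed scheduled tumor assessment". For everyone else, "Patients without metastasis and death are censored at the date of the last disease assessment". Patients with no post-baseline assessment are censored at randomization.

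The analysis is one line in SAP 7.6.2.4: "DMFS will be analyzed using the same methods described for OS/PFS". Those methods (SAP 7.6 and 7.6.1.1) are Kaplan-Meier by arm on the ITT set, with an exploratory hazard ratio and stratified log-rank test. The ITT set is all randomized patients (SAP 6.1).

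On eligibility, inclusion criterion 1 in Protocol 6.1 reads "Locally advanced, relapsed, or metastatic sarcoma with measurable tumor burden following therapy". Disease status at study start and stage M are among the baseline characteristics to be tabulated (SAP 7.5). SAP 7.7 uses the split into locally advanced and metastatic disease, but introduces its subgroups as being for the PFS and OS analyses.

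On imaging, footnote b to Protocol Tables 1 and 2 schedules tumor assessment until progression and adds "Patients will then have no further staging procedures". Protocol 8.2.3.1 describes visits that include CT staging and run to the later of one year and progression.

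**The concern.** Metastasis-free survival presupposes that the patient is metastasis-free when the clock starts. In a trial that enrols metastatic sarcoma, many patients may not be. For them the endpoint can record only an additional distant lesion or an early death. Growth of the metastases they brought into the trial is never an event.

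The reported curve would blend two quantities under one name: time to first distant spread in patients who had none, and time to a further distant lesion in patients who did. A reader who sees a DMFS median or a log-rank p-value would naturally take it as evidence on prevention of distant spread. In the metastatic patients it cannot be that.

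A second, less certain issue is follow-up. Scans generally end at progression, and SAP 5.1.2.4 does not say what happens to a patient who progresses by growth alone, or to one who dies after two or more missed assessments.

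**Working it through.** **No plan figure to reproduce.** Neither document gives a sample size, expected rate or event count for DMFS. The main step is therefore a reading of the rules.

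**Step 1: apply the rules to three patients.**

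| Patient | Status on Day 0 | Course | Result under SAP 5.1.2.4 |
|---|---|---|---|
| A | No distant metastasis | New distant lesion | Event; matches the name |
| B | Distant metastases | Existing lesions grow, none new | No event; counted metastasis-free up to the last assessment |
| C | Distant metastases | Further distant lesion | Event; records additional spread, not first spread |

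B and C are in the ITT set and contribute to the curve at 100% on Day 0. This step needs no assumption.

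**Step 2: how many patients fit the name.** Planned size is about 40 per arm (Protocol 10.3.1; SAP 4). With a share f metastatic at entry, the number at risk of first distant spread is 40 × (1 − f). The documents do not give f. Assumed values:

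- f = 0.5: 40 × 0.5 = 20 per arm
- f = 0.7: 40 × 0.3 = 12 per arm
- f = 0.9: 40 × 0.1 = 4 per arm

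**Step 3: can the censoring bias be signed?** Take the plan's exponential PFS with median 5.2 months: λ = ln 2 / 5.2 = 0.1333 per month. Assume half of first events are growth without a new distant lesion. The hazard of a new distant lesion or death is then 0.0667 per month, and the same for growth-only progression. Censoring at growth-only progression gives a 12-month estimate of exp(−0.0667 × 12) = 0.45.

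- If the hazard of metastasis or death is unchanged after progression, the true value is also 0.45, so there is no bias.
- If that hazard doubles, the true value is exp(−0.1333 × 12) × (1 + 0.0667 × 12) = 0.202 × 1.80 = 0.36, so the estimate is 9 points too high.

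Over PFS medians of 3 and 5.2 months, growth-only shares of 30% to 70% and hazard ratios of 2 to 3, the 12-month overstatement runs from about 5 to 23 points.

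This model ignores an opposing effect. If deaths close to the last scan are counted at the death date while later survivors are censored back at that scan, early deaths are over-represented and the curve is pulled down. The net direction depends on quantities that the documents do not supply.

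**Step 4: would counting every death repair it?** Assume median PFS 3 months, 25% of progressions distant, median survival after progression 12 months, a last scan one month after progression, and a 91-day death window borrowed from the PFS rule in SAP 5.1.1.1. By simulation the median is about 8.5 months under the near-scan-death rule and 12.1 months with all deaths counted. Now allow new distant lesions after progression, with median time 3, 6 or 12 months. The true median becomes 5.6, 6.9 or 8.3 months, each nearer to 8.5 than to 12.1.

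The same comparison was made over 2 PFS medians × 2 distant shares (25%, 50%) × 2 survival medians (6, 12 months) × 3 metastasis times = 24 settings. In all 24, counting every death was further from the truth. With scanning stopped, it credits unscanned patients as metastasis-free until they die.

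**The case against.** The best defence is that SAP 5.1.2.4 says openly that the event is a new lesion, so the quantity is defined and computable. Randomization makes the ITT comparison fair for that quantity. All p-values are nominal (Protocol 10.4), between-arm comparisons are exploratory (SAP 7.9), and no design decision uses DMFS. SAP 5.1.3.4 already plans a time-to-new-lesion analysis with death as an event. One might also argue that borrowing the OS/PFS methods brings in the forest plot by disease status.

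Much of this stands, and it limits the importance of the point. It does not correct the label. SAP 7.7 confines its subgroups to PFS and OS, and a forest-plot row would leave the headline DMFS estimate unchanged. The time-to-new-lesion endpoint is not restricted to distant sites.

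Three stronger readings are tempting, and the documents do not support them:

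- **That late deaths are lost by rule.** SAP 5.1.2.4 gives no explicit rule for them. The 91-day cut-off belongs to PFS. If no scan is scheduled after progression, none can be missed, so a later death could literally count.
- **That scanning always ends at progression.** Protocol 8.2.3.1 reads otherwise for part of the first year. Protocol 6.3 lets some patients continue treatment after confirmed progression, with no scan schedule stated for them.
- **That the secondary objective goes wholly unanswered.** DMFS is meaningful in patients without distant metastasis at entry.

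**Conclusion.** The mismatch between name and population holds on the text alone: metastatic patients are eligible, all randomized patients enter the DMFS analysis, and no DMFS rule separates those metastatic at baseline. The ITT curve and log-rank test should not be reported as distant metastasis-free survival.

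The size in patient numbers rests on an assumed metastatic share. At 50% to 90%, about 20 to 4 of 40 per arm match the endpoint's name. A reader might infer that censoring at progression biases DMFS in a known direction or by a known amount. Steps 3 and 4 show that this depends on post-progression risks that the documents do not give, so no magnitude should be attached to it. What can be said is that the handling of late deaths and of growth-only progression is undefined. The point merits correction, but does not threaten the trial's primary analyses.

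**What to change.** In SAP 5.1.2.4 and 7.6.2.4:

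1. Analyse DMFS in randomized patients without distant metastasis at baseline. Name the variable that decides membership; stage M and disease status at study start are already collected (SAP 7.5).
2. Report the ITT version as *time to first new distant lesion or death while under scan follow-up*, split by baseline metastatic status.
3. State one rule for deaths after two or more missed assessments and one for progression without a new distant lesion.
4. Add a sensitivity analysis that counts all deaths. Do not make it the main rule while scans generally stop at progression.
5. Reconcile footnote b of Protocol Tables 1 and 2 with Protocol 8.2.3.1 on when staging ends, and describe the outcome in the SAP.

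The cost is wording, one subset analysis, a split of the ITT output and one sensitivity output, with no new data collection. The drawback is precision: with perhaps 4 to 20 patients per arm under the assumed shares, the subset may support only a descriptive estimate.

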# 5.1.3 Exploratory Efficacy Endpoints

# 5.1.3.1 Tumor Growth Rate and Progression Arrest Rate

Progression status as determined by investigator performed by using outside images off protocol at screening will be collected in study.

At the baseline tumor assessment, the sum of the longest diameters (SLD) of all index lesions (2 target lesions per organ, up to 5 target lesions in total) will be calculated. At each subsequent tumor assessment, the SLD of the index lesions and of new, measurable lesions is calculated: SLD = SLD index lesions + SLD new, measurable lesions

Percentage changes in SLD per assessment time point describe the size and growth kinetics of both conventional and new, measurable lesions as they appear.

# 5.1.3.2 Overall Response Rate (ORR) and Duration of Response (DOR)

Overall response rate (ORR) will be defined as the number of patients whose best overall response is complete response (irCR) or partial response (irPR) divided by the number of evaluable patients. Overall response rate based on unconfirmed response and confirmed response will both be summarized.

Duration of response (DOR) will be defined only for the patients whose confirmed best response is irCR or irPR as the time interval between the date of the earliest qualifying confirmed response and the date of progressive disease (PD) or death for any cause, whichever occurs first. DOR in months will be calculated as: (date of PD or death, whichever occurs first – date of first confirmed irCR or irPR + 1)/30.4375.

For patients who are alive without documentation of disease progression following the qualifying response, duration of response will be censored following the same rule defined for PFS.

# 5.1.3.3 Clinical Benefit Rate (CBR) and Duration of Clinical Benefit

Clinical benefit rate (CBR) will be defined as the number of patients whose best overall response is complete response (irCR), partial response (irPR) or stable disease (irSD) divided by the number of evaluable patients. Clinical benefit rate based on unconfirmed response and confirmed response will both be summarized.

Duration of clinical benefit will be defined only for the patients whose confirmed best response is irCR, irPR or irSD as the time interval between the date of the earliest qualifying confirmed response and the date of progression disease (PD) or death for any cause, whichever occurs first. Duration of clinical benefit in months will be calculated as: (date of PD or death, whichever occurs first – date of first confirmed irCR, irPR or irSD + 1)/30.4375. For patients who are alive without documentation of disease progression following the qualifying response, duration of clinical benefit will be censored following the same rule defined for PFS.

#### 5.1.3.4 Time to New Lesion

Two time to new lesion definitions are included in the analysis: one excludes death, the other includes death as an event.

- Definition 1: calculated as (first new lesion scan date date of randomization + 1)/30.4375. Patients without new lesion scanned are censored at the date of the last disease assessment. Patients without post-baseline disease assessment are censored at randomization date.
- Definition 2: calculated as (first new lesion scan date or death date within 2 missed scheduled tumor assessment date of randomization + 1)/30.4375. Patients without new lesion scanned and death are censored at the date of the last disease assessment. Patients without post-baseline disease assessment are censored at randomization date.

## 5.2 Safety Endpoints

The safety endpoints for the study include the nature, frequency, and severity of adverse events and clinically significant abnormalities. Laboratory tests, vital signs, ECOG performance status, physical exams, and 12-lead ECG will be summarized and/or analyzed to inspect for trends of abnormalities and deteriorations of any pre-existing conditions.

All clinically significant abnormalities and deteriorations identified in laboratory tests, vital signs, physical exams and 12-lead ECG will be entered in the case report forms (CRFs) as Adverse Events and graded according to the NCI CTCAE v4.03.

# 6 ANALYSIS SET

#### 6.1 Intent-to-Treat Set

The Intent-to-treat (ITT) analysis set consists of all randomized patients. All analyses of this set will be based on the treatment arm to which the subjects are randomized.

# 6.2 Safety Set

The Safety analysis set includes all enrolled patients who received any of the CMB305 components (LV305, G305) or atezolizumab. The Safety analysis set is the primary set for safety analyses including adverse events (AEs) and clinical laboratory data. Trial product exposure will also be summarized using the Safety set.

# 6.3 Efficacy Set

The Efficacy analysis set includes all randomized patients who have received at least one injection/dose of any of the CMB305 components (LV305 and G305) or atezolizumab and had at least one post-baseline scan or discontinued or died prior to 2 missed tumor assessments.

# 7 STATISTICAL ANALYSES

#### 7.1 Data Summaries and Conventions

All data collected on CRFs will be provided in listings, except data collected only for confirmation of study entry criteria and for study administrative purposes. If any enrolled patient is found to not have valid documented informed consent, that patient's data will be excluded from the report, except as necessary to document the error.

Except where specified all continuous variables will be summarized with descriptive statistics (the number of non-missing values, mean, standard deviation, median, minimum and maximum) and all categorical variables will be summarized with frequency counts and percentages, by treatment arm (combination arm vs. control arm).

## 7.2 Missing Data

For adverse events and concomitant medication, the imputation rule for start date and end date are defined in below section. For other analysis when necessary (e.g., OS analysis), dates without a specific day of the month (i.e., JAN2010) will be assigned the 15th day of the month and dates without a specific day or month (i.e., 2010) will be assigned the 15th day of June.

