#### IMDZ-C232

On-study radiotherapy and surgeries should continue to be recorded until documented radiographic progression, even if progression occurs after study treatment discontinuation. Non-protocol systemic anti-cancer therapies administered before documented radiographic progression should be recorded as concomitant medications.

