# **5 STUDY ENDPOINTS**

# 5.1 Efficacy Endpoints

# 5.1.1 Primary Efficacy Endpoint

# 5.1.1.1 **Progression free Survival (PFS)**

PFS will be based on RECIST 1.1 response guidelines modified to use irRC-specific confirmation. Progression-free survival (PFS) in months is calculated as: (date of first progression or death (any reason) – date of randomization +1)/30.4375. The irRC modification requires a confirmation of progressive disease (PD) at least 4 weeks later with imaging; once confirmed, the date of progression is defined as the first date the total tumor burden was shown to have increased by at least 20% compared with nadir. Patients without progression or death are censored at the date of the last disease assessment. If a patient begins a new anti-cancer therapy or has radiotherapy or surgery at a lesion site prior to confirmed progression (or death), the patient will be censored at the last assessment where the patient was documented as progression free prior to the intervention. Patients with two or more missing response assessments prior to a visit with progression (or death) will be censored at the last visit where the patient is documented to be progression free. Patients without disease assessment post-baseline will be censored at the randomization date. As needed, we will use Table 3 to specify how dates of progression events and dates for censoring of progression data are assigned. Table 3 represents an analysis that only includes well-documented and verifiable progression events. In Table 3, the progression dates are:

- Based only on radiological assessments verified by an IRC and symptomatic deterioration date assessed by study investigator.
- Assigned to the first time when tumor progression was noted.
- The date of death when the patient is closely followed. However, deaths occurring after two or more missed tumor assessments (> 91 days after last tumor assessment) are censored at the last visit.

Progressive disease will be assessed by the unidimensional measurements approach of the Immune-related Response Criteria.

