#### 7.2.2 Partial Dates for Concomitant Medication

For medications with incomplete dates, imputation will be used to convert to a complete date. Imputed dates will be used to determine Study Day.

Partial medication start dates will be imputed as follows:

- 1. Only the year is reported: If the subject started to receive study drug in the year reported, then the date of the first dose of study drug will be used as the starting date of the medication. Otherwise, January 1 will be used as the start of the medication.
- 2. The month and year are reported: If the subject started to receive study drug during the month and year reported, then the date of first dose of study drug will be used as the starting date of the medication. Otherwise, the first day of the month will be used as the start of the medication.

Partial medication end dates will be imputed for non-ongoing medications as follows:

1. Only the year is reported: If the subject stopped to receive study drug in the year reported, then the date of the last dose of study drug will be used as the end date of the medication. Otherwise, December 31 will be used as the end of the medication.

2. The month and year is reported: If the subject stopped to receive study drug during the month and year reported, then the date of last dose of study drug will be used as the end date of the medication. Otherwise, the last day of the month will be used as the end of the medication.

If an imputation results in an imputed start date after the stop date, the start date will be set to the day prior to the stop date.

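### SAP 7.2 sets partial dates to the 15th or 15 June without limits from recorded dates, so an imputed death can precede last contact and an imputed therapy start can precede the progression scan

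*SAP*

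**What the plan says.** SAP section 7.2 gives adverse events and concomitant medications their own rules and then covers the rest: "For other analysis when necessary (e.g., OS analysis"). The rule for a missing day is that "dates without a specific day of the month (i.e., JAN2010) will be assigned the 15th day of the month". Where the month is missing as well, the SAP's instruction is: "dates without a specific day or month (i.e., 2010) will be assigned the 15th day of June". It sets no limit from randomization, last contact, last dose, scan dates or data cut-off. The protocol has no imputation rule; its section 10.2 leaves data handling to the SAP.

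Three endpoints use such dates directly:

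- **OS (SAP 5.1.1.2)** runs from randomization to the date of death. The last-known-alive date is used only to censor living patients.
- **PFS (SAP 5.1.1.1 and Table 3)** depends on order. The rule begins "If a patient begins a new anti-cancer therapy or has radiotherapy or surgery at a lesion site prior to confirmed progression (or death"). The consequence it sets is that "the patient will be censored at the last assessment where the patient was documented as progression free prior to the intervention".
- **TTNT (SAP 5.1.2.3)** runs to the start date of subsequent therapy.

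SAP 7.2.2 has a different rule for concomitant-medication start dates. If the month matches the first dose, the first-dose date is used. "Otherwise, the first day of the month will be used as the start of the medication". Its one ordering check is that start must come before stop. SAP 3.1 adds that "Non-protocol systemic anti-cancer therapies administered before documented radiographic progression should be recorded as concomitant medications". The SAP does not say which of the two rules supplies therapy dates to PFS and TTNT.

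**The concern.** A mid-point rule is a reasonable default, but it needs limits when other recorded dates restrict the answer. Here it has none, and both primary endpoints are exposed.

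For OS, the rule can contradict the trial's own data by dating a death before a visit at which the patient was alive, or before randomization.

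For PFS, the problem is order as well as duration. A therapy that truly followed progression can be imputed to a date before it. The patient then changes from an event to a censoring at an earlier scan. Each such change removes an event, which tends to raise the Kaplan-Meier PFS curve and, if the event fell before 6 months, the 6-month progression-free rate. TTNT is shortened at the same time.

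Partial dates are plausible. Deaths are documented by local physicians or registries (SAP 3.1). Later treatments come from quarterly calls or database searches (protocol 8.2.4).

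**Working it through.** The plan gives no figure to reproduce. The check applies its rules to example dates, which are chosen for illustration.

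**Inputs.** Day missing becomes the 15th, and month missing becomes 15 June (SAP 7.2). Time in months = (date − randomization + 1)/30.4375 (SAP 5.1.1.1, 5.1.1.2). Scans are every 6 weeks in year 1, and confirmation comes at least 4 weeks later (SAP 3.1).

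**1. Largest shift.** Day missing: the 31st becomes the 15th, so 31 − 15 = 16 days early. Month missing: 15 June is day 166, so 365 − 166 = 199 days early.

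**2. OS examples.**

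| Randomized | Last known alive | Death recorded | Imputed | OS as imputed | OS must be at least |
|---|---|---|---|---|---|
| 10 Jan 2017 | 24 Jan 2018 | JAN2018 | 15 Jan 2018 | 371/30.4375 = 12.19 | 380/30.4375 = 12.48 |
| 10 Jan 2017 | 1 Nov 2018 | 2018 | 15 Jun 2018 | 522/30.4375 = 17.15 | 661/30.4375 = 21.72 |
| 10 Aug 2017 | – | 2017 | 15 Jun 2017 | −55/30.4375 = −1.81 | above 0 |

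**3. How often a partial death date conflicts.** Assume last contact was 0 to 30 days before death, all gaps equally likely.

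- Day missing, 30-day month: a conflict needs last contact after the 15th and death in the same month. That is 15 − g starting days for gap g = 0 to 14, so (15 + 14 + … + 1)/(31 × 30) = 120/930 = 13%.
- Month missing: the sum of (199 − g) for g = 0 to 30, divided by 31 × 365, is 5704/11315 = 50%.

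**4. PFS example.** Randomized 10 Jan 2017, clear scan 9 May, progression scan 20 June (later confirmed), therapy recorded as JUN2017 and truly started after the scan. It is imputed to 15 June, before the scan. The event at 162/30.4375 = 5.32 months becomes a censoring at 120/30.4375 = 3.94 months. This takes the censoring trigger to be therapy before the first progression scan.

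**5. How often the order reverses.** Scan before therapy, both in one month of L days, therapy day missing, all ordered pairs equally likely. The order reverses when the scan is after the 15th: C(L−15, 2)/C(L, 2).

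- L = 28: 78/378 = 20.6%
- L = 30: 105/435 = 24.1%
- L = 31: 120/465 = 25.8%
- Month also missing, same year: C(199, 2)/C(365, 2) = 29.7%

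For a fixed gap of g days and a uniform scan day in a 30-day month, the share is (15 − g)/30, with a floor of 0:

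| Gap (days) | 3 | 7 | 14 | 21 |
|---|---|---|---|---|
| Reversed | 40% | 27% | 3% | 0% |

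With only the year known, the share is (199 − g)/365: 54% at 3 days and 49% at 21 days.

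**6. Which scan counts.** The SAP dates progression at the first scan with the 20% increase but words the trigger around confirmed progression.

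- Against the first scan, the gaps in step 5 run from that scan.
- Against the confirmatory scan, therapy started between the two scans is censored even with complete dates, so imputation matters only near the confirmatory scan. For gaps of 1 to 28 days after it, the sum of (15 − g)/30 averages to 105/(28 × 30) = 12.5%; for 1 to 14 days, 105/(14 × 30) = 25%.
- Therapy that starts after confirmation is at least 29 days after the first scan. A missing day moves it at most 16 days, so it cannot pass the first scan.

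**The case against.** **A larger PFS effect does not follow.** A reader might infer that post-progression chemotherapy takes the first-of-month rule in SAP 7.2.2, which would reverse about 93% of same-month pairs (C(29, 2)/C(30, 2) = 406/435), or that a year-only date becomes the first-dose date and censors the patient at baseline. The documents do not support this. SAP 3.1 sends only systemic therapies given before documented radiographic progression to the concomitant-medication record, and for those censoring is generally what the PFS rule intends. Therapy after progression is subsequent therapy (SAP 7.8.11). SAP 7.2.2 states that its imputed dates serve to determine study day, and nothing links them to PFS. What remains is that the SAP never says which rule governs anti-cancer therapy dates.

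**Every percentage is conditional on a partial date**, and the number of these is unknown. Protocol 9.4.5 requires deaths from progression to be reported as SAEs within 24 hours, 9.4.7 commits to attempts to establish the date of death, and section 12.0 provides for consistency review and queries. Follow-up every 3 months makes a year-only death the least likely case, yet that case gives the largest shifts. This lowers the expected frequency but does not supply a bound.

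**The stakes are moderate.** The primary analyses are Kaplan-Meier estimates by arm, comparisons are exploratory, and the same rule applies to both arms. This stands.

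**A bound could be added in the dataset specifications** that SAP section 1 mentions. But 7.2 is explicit, so a bound added there would depart from the SAP and might be chosen with outcomes in view.

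**Conclusion.** The point holds as a should-fix. SAP 7.2 states a rule that, followed literally, can produce OS times contradicted by the trial's own records, including negative ones. This half needs no assumption beyond the existence of a partial death date.

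The PFS and TTNT half also holds, but its size varies. With the day missing, reversal requires scan and therapy in the same month with the scan after the 15th. It falls from 40% at a 3-day gap to 0% at 21 days in a 30-day month. It also depends on whether the trigger is judged against the first or the confirmatory scan. These rates assume uniform calendar dates.

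A reader might conclude that median PFS, median OS or the 6-month rate is materially biased. The documents give no count of partial dates, so that cannot be computed. With about 40 patients per arm, a few patients is the probable extent. Nor is it correct that the SAP has no bounds at all: 7.2.2 has some, but none refers to progression or last contact.

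**What to change.** Amend SAP 7.2 before database lock:

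1. **Death.** Use the later of the mid-point date and the last-known-alive date plus 1 day, within the reported month or year and not after data cut-off. In the first two OS examples this gives 381/30.4375 = 12.52 and 662/30.4375 = 21.75 months. If last contact falls outside the reported period, query the record.
2. **Anti-cancer therapy.** State that dates used for PFS and TTNT follow 7.2, not 7.2.2. Bound them to the reported month or year, not before randomization, and not after death or cut-off. For post-treatment systemic therapy only, add a floor at the last study-drug dose. Leave radiotherapy and surgery out of that floor, because protocol 7.4.2 allows local treatment while study drug continues.
3. **Order.** Where the record shows that a therapy was given after documented progression, do not let the imputed date reverse that order. Where the order is unknown, pre-specify one handling and run a sensitivity analysis the other way; always counting the progression would be a preference with its own bias.
4. **Trigger.** Say whether the PFS censoring rule refers to the first progression scan or the confirmatory one.

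The cost is a few sentences, changes to the date derivations and one sensitivity run. No new data are needed.
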